1.0 PROTOCOL SUMMARY AND/OR SCHEMA

Title: Feasibility and Effectiveness of Automated Geriatric Co-Management Program on Improving the Perioperative Care of Older Patients with Solid Mass or Nodule Suspicious for Cancer

Study Center: MSKCC

Expected Time to Study Completion: 24 months

Objectives:
 
Primary objective: To determine the feasibility of automated geriatric co-management program in the care of geriatric oncology patients.
 
Secondary objectives:
 
• To compare the effect of automated geriatric co-management program with in-person geriatric co-management on adverse surgical events.• To compare the effect of automated geriatric co-management program with in-person geriatric co-management on postoperative functional recovery.

Study Design:
 
• Prospective Randomized Trial• Patients will be randomized 1:1 to receive either automated geriatric co-management during surgery visit when they are considered for surgery, or to be referred to geriatrics service for in-person geriatric co-management which can be done either in the clinic or via telemedicine.

Study Population
 
Patients with a solid mass or nodule aged 65 or older who are presenting to MSKCC's surgery clinics for consideration of surgery.
 
Number of patients: 77 patients evaluable in the automated arm, estimated to be 200 patients in the study

Inclusion and Exclusion Criteria:
 
Inclusion:
 
1) Solid mass or nodule suspicious for cancer,2) Aged 65 or older,3) Being considered for surgical resection of the solid mass or nodule, with anticipated hospital length of stay of at least two days,4) Completed Electronic Rapid Fitness Assessment 
Exclusion:
 
1) Unable to read or comprehend English2) Not having a completed electronic Rapid Fitness Assessment within 2 months of surgery3) Being discharged in one day or earlier from the hospital

Figure 1- Study schema

2.0 OBJECTIVES AND SCIENTIFIC AIMS

Aim 1: To determine the feasibility of *automated geriatric co-management program* in the care of geriatric oncology patients.

The feasibility of the program will be assessed by the percentage of patients in whom at least half of the recommendations made by the program are followed by the surgical team. Our program will be deemed **feasible** if at least 50% of recommendations are followed in at least 70% of patients with impairments.

We based our cutoff based on multiple studies. A study done on surgeons' attitude toward assessment and management of older cancer patients, Ghignone et al[1], showed that only 6.4% of surgeons use geriatric assessment in their daily practice and only 36% collaborate with geriatricians in some form. Studies on geriatric comanagement of older adults who are receiving chemotherapy also showed that the pickup rate of interventions by the medical oncologists is around 35% [2]. Given these findings, we hypothesized that a more than 50% adoption of recommendations would be a reasonable rate for then refining the intervention and conducting an R01 study in the future.

Aim 2: To compare the effect of *automated geriatric co-management* program with in-person geriatric co-management on adverse surgical events.

Aim 3: To compare the effect of automated geriatric co-management program with in-person geriatric co-management on postoperative functional recovery.

3.1 BACKGROUND AND RATIONALE

Surgery remains the mainstay of cure for many older cancer patients.[3] As cancer incidence increases with age and with an aging population, it is expected that more older adults will be diagnosed with cancer.[4] Further, with the approval of lung cancer screening by Medicare, in addition to other cancer screening recommendations such as colonoscopy, it is expected that more older patients be diagnosed with cancer at an earlier stage.[5]

Older Cancer Patients and Surgical Outcomes: Prediction

Older and especially older frail cancer patients are at a highest risk for adverse surgical events and slower functional recovery following cancer surgery.[6] In an attempt to assess and lower the risk of a procedure for a patient, the American College of Surgeons and the American Geriatrics Society recommend incorporating geriatric assessment (GA) into the preoperative evaluation.[7] The goal of the GA is to identify geriatric syndromes and manage them perioperatively.[8] Studies have shown that components of GA are associated with the surgical outcomes. For example, a study of 120 patients aged 60 years or older who underwent thoracic surgery (85 of whom had lung cancer) showed that patients with dependency for performing basic activities of daily living (bADL) and those with dementia were more likely to develop postoperative complications.[9]

The Modified Frailty Index (m-FI) is a frailty index based on the American College of Surgeons National Surgical Quality Improvement Project.[10] It is a mix of 10 comorbid and medical conditions and one item on the level of independence for bADL and instrumental activities of daily living (iADL). The score runs from 0 to 11 and the score of 3 or higher is considered as frail. A study of 1940 patients who underwent thoracotomies and lung lobectomy showed that 5.6% of frail patients died after surgery compared to just 1% of fit patients. Moreover, major complications occurred in 4.2% of fit patients compared to 14.4% of frail patients.[11]

In addition to studies specific for oncologic thoracic surgery procedures, other studies have shown the same correlation with postoperative outcomes of other oncologic surgical procedures. A recent systematic review found that six separate prospective studies assessed the correlation between components of the GA and adverse surgical outcomes of older cancer patients. These studies confirmed that impairments in bADL, iADL and cognitive function are associated with an increased risk of postoperative complications.[12]

Interventions Aimed at Improving Surgical Outcomes of Older Patients: Collaboration between Surgeons and Geriatricians

It is important to note that identification of geriatric syndromes without appropriate perioperative interventions to manage the detected deficits will not improve surgical outcomes. In non-oncologic surgery setting, collaboration between surgeons and geriatricians has led to significant improvement in surgical outcomes by identifying and managing geriatric syndromes. In a study on 297 patients aged 70 years or older who underwent hip surgery, patients were randomly assigned to postoperative care in a geriatric ward vs. routine care in a surgical ward. At one and four months after surgery, patients in the geriatric ward showed more improvement in their mobility as measured by Short Physical Performance Battery, than patients in the surgical ward.[13] In another trial, 162 patients with hip fractures were randomized to geriatric consultation and care before and after surgery during the hospital course vs. care by the surgical team alone.[14] Patients in the intervention group experienced better performance on iADL, recovery of walking ability, fewer falls, fewer depressive symptoms and better quality of life during the first 24 months after hospital discharge. Another study on 319 patients aged 65 years or older who underwent hip fracture surgery showed that geriatric co-management after surgery can reduce in-hospital mortality from 5.8% to 0.6%, and reduce complication rates from 61% to 45%. Notably, this study showed that 57% of patients in the intervention group achieved partial or complete recovery compared to 44% in the control group.[15]

Limitations of Current Evidence in the Cancer Setting:

There is only very limited data on the effectiveness of such collaborations between surgical oncologist and geriatricians. In one study on oncologic surgeons' attitude toward perioperative care for older adults with cancer, among 11% who responded to the survey, only one out of three surgeons stated that they routinely collaborate with geriatricians.

The reasons for such a low rate of collaboration is likely multi-faceted. **First**, there is a shortage of geriatricians with only 7000 practicing in the United States.[16] **Second**, with geriatricians involved in various other critical initiatives such as long-term care or caring for older patients with Alzheimer, only limited time may be available to provide postoperative geriatric co-management for older cancer patients routinely.

The shortage of geriatricians could be addressed in two ways:

- 1- by training more providers, either geriatricians or geriatric nurse practitioners: This will be costly, requires significant amount of time and effort, and will not be available to provide an immediate answer to such need.
- 2- by providing surgeons with easy to administer GA and developing an ***Automated Geriatric Co-management Program***, which will automatically provide geriatric recommendations based on impairments found via the GA to the surgical team. If this

program is shown to be feasible, acceptable to treating clinicians, and as effective in improving surgical outcomes as in-person geriatric co-management, then it can be adopted by all institutions that have limited or no geriatric service resources.

In summary, the rationale for this project is as follows.

- 1- The US population is aging.
- 2- The Incidence of cancer increases with age.
- 3- The introduction of cancer screening such as lung cancer screening will further increase the number of older adults with early stage cancer increases in the near future.
- 4- Surgery is the mainstay of cure for early stage cancer patients.
- 5- The likelihood of adverse surgical events and slow functional recovery increases in older adults, and especially older frail adults with cancer.
- 6- Geriatric Assessment can assess patient frailty and identify potentially manageable geriatric syndromes.
- 7- Management of geriatric syndromes can lead to improved surgical outcomes.
- 8- Collaboration between non-oncologic surgeons and geriatricians to manage geriatrics syndromes have substantially improved surgical outcomes.
- 9- Even if such collaboration is effective, it may not be scalable due to a limited number of geriatric healthcare providers.

As a result, an automated geriatric co-management program, if shown to be feasible and as effective as in-person geriatric co-management, could be used to provide peri-operative geriatric care routinely in institutions that have limited or no geriatrics services.

The Electronic Rapid Fitness Assessment (the eRFA) at Memorial Sloan Kettering Cancer Center (MSKCC)

The eRFA was developed at MSKCC through collaboration between the Geriatrics Service and the Web Survey Core Facility (Webcore) in 2015. During the eRFA development process, the Geriatrics Service held multiple discussions to determine which GA domains to assess and which validated assessment methods to use. The name “Electronic Rapid Fitness Assessment” was selected to reflect the purpose of the GA, which is to distinguish patients who are fit from those who are frail.

Administration and Reporting of the eRFA:

The eRFA was first implemented in the Geriatrics clinic. In 2016, the Thoracic surgery clinic implemented the eRFA at the point of care. All patients who present to MSKCC geriatric clinics or thoracic surgery clinics complete the eRFA while they are waiting to be seen by their healthcare providers for their initial consultation. Patients may complete the eRFA on their own or with assistance from others (e.g., a caregiver), or they may allow someone else

(e.g., a caregiver) to complete the assessment for them. Patients may also complete the eRFA at home, before their appointment, if they have Internet access and an e-mail account. After the assessment has been completed, a registered nurse (RN) performs a cognitive assessment using the Mini-Cog[17, 18] and establishes the patient's mobility using the Timed Up and Go (TUG)[19] test, the results of which are then entered into the eRFA by the RN. The Mini-Cog and TUG assessments will be omitted if the patient is being seen via telemedicine.

The eRFA contains 28 questions about functional status, cognition, social support, social activity interference, emotional status, nutrition, vision, hearing and polypharmacy. On average, it takes between 10 to 20 minutes to complete. The eRFA is accessible using computers, tablets, and smartphones. It is partially integrated with the electronic medical record (EMR), with patients' names and medical record numbers pulled from the EMR as patient-specific questionnaires are generated.

The components of the eRFA, the 12 major instruments utilized, and the cutoff for significantly abnormal values are shown in figure 2.

Figure 2. Twelve major instruments of Electronic Rapid Fitness Assessment (the eRFA)

Domain	Instrument	Completed by	Description	Score range	Frail values
Functional Domain	Activities of Daily Living (ADL) [20]	Patient	Basic Activities of Daily Living (bADL or ADL) assesses patients' level of independence in 7 activities: bathing, dressing, grooming, feeding, bladder and bowel control, and walking inside and outside of the house. Answer choices to each are: limited a lot (0), limited a little (1), not limited (2).	0-14	≤13
	Instrumental Activities of Daily Living (iADL) [21]	Patient	Instrumental Activities of Daily Living (iADL) assesses patients' level of independence in 8 activities: telephone use, doing laundry, shopping, preparing meals, doing housework, handling own medications, handling money and finances, and transportation. Answer choices to each are: unable to do (0), able with some help (1), able without help (2).	0-16	≤15
	Karnofsky Performance Status (KPS) [22]	Patient	Karnofsky Performance Status rates patient's functional independence in performing ordinary tasks. The score ranges from 100 (Normal with no symptoms) to 0 (Dead) in increments of 10.	30-100	≤80

The patient-rated KPS is answered in 8 levels:

			100- Normal, no symptoms 90- Able to carry on normal activity, minor symptoms 80- Normal activity, with effort, some symptoms of disease 70- Can care for self, but unable to do normal activity or work 60- Require occasional assistance, but able to care for most needs 50- Require considerable assistance 40- Disabled, require special care and assistance 30- Severely disabled, require continuous nursing care		
	Fall in the past year	Patient	The number of falls in the past year	None, One time, More than one time	≥ 1 time
	Timed Up and Go test [19]	Nurse	Patients are asked to stand from the chair, walk ten feet, turn and return to the chair. The total time is recorded.	<10 seconds, 10-19 seconds, ≥ 20 seconds	≥ 10 seconds
Social support/activity	Social support survey [23]	Patient	The Medical Outcome Study- Social Support Survey- 4 item asks 4 questions on how often patients have someone to receive support from: All the time (5), Most of the time (4), Some of the time (3), A little of the time (2), Not at all (1). Higher scores mean better social support.	4-20	≤ 16
	Social activity limitation [24]	Patient	The Medical Outcome Study- Social Activity Survey asks how much patients' social activity is limited and how much often it has become limited/ interfered with recently. 3 questions with 5 answers (1-5) are counted. Higher scores mean more limited social activity.	3-15	≥ 8
Cognition	Mini Cog test [17, 18]	Nurse	Patients are told three words to memorize. Then they are asked to draw a clock with hands showing ten past eleven. Then they are asked to recall the three words. Clock draw is evaluated either normal with 2 points or abnormal with 0 point. Each correctly recalled word has 1 point (0-3).	0-5	≤ 2

Emotional wellbeing	Distress [25]	Patient	The Distress Thermometer ranges from 1 (no distress) to 10 (extreme distress).	1-10	≥ 4
	Depression [26, 27]	Patient	The Geriatric Depression Scale- 4 item is a yes/no questionnaire. Patients receive 1 point for each answer that indicates depression.	0-4	≥ 1
Poly-pharmacy	Poly-pharmacy [28]	Patient	The number of medications currently taken	1-4 medications, 5-9 medications, ≥ 10 medications	≥ 5 medications
Nutritional status	Weight change	Patient	Weight change in the past 6 months	no change or weight gain, lost < 5 lbs, lost 5-10 lbs, lost 10-20 lbs, lost ≥ 20 lbs	lost ≥ 10 pounds

The eRFA in the Thoracic Surgery Clinics as a Model for other Surgical Clinics:

After development and successful implementation of the eRFA in all MSKCC Geriatric clinics[29], more than 4000 older cancer patients with a median age of 80 have completed the eRFA. Patients have shown very high levels of satisfaction with the instrument, and, as a result, thoracic surgery clinics have implemented the eRFA in their clinics as a routine care for the new patients. We have shown that implementation of eRFA in the thoracic surgery clinics is feasible and can yield useful clinical information that can be managed perioperatively.[30]

For the purpose of this study, thirteen comorbid conditions are queried and combined as one item in addition to the 12 items in the eRFA report.

Throughout the study, we have realized the most limiting factor in efficiently accruing patients was very strict inclusion and exclusion criteria that required a significant amount of time from research coordinators, and healthcare providers to properly assess these patients. Because this is a pilot study, based on R21 study, we have realized that such strict inclusion and exclusion criteria are not needed at this time.

Thus far, we have made significant improvements in the study process itself. For example, in the beginning, the electronic Rapid Fitness Assessment was on the Webcore platform with limited resources. Over the past months, we have moved to MSK Engage platform, and further enhanced our collaboration with the Engage team, which has more supportive staff than the Webcore platform.

During the course of the study, The PI has given lectures to various surgery services about the importance of assessing fitness/frailty of older adults with cancer before surgery and the need to properly optimize the status of these patients. These lectures were met with significant enthusiasm and surgeons expressed the desire to be able to accrue patients for this study.

Finally, proper assessment of fitness/frailty of older adults with cancer is not unique to one disease or one surgery service. In fact, frailty is considered a global syndrome without sociodemographic or clinical boundaries. As a result, in order to allow patients with other diseases who are going to undergo various surgeries to be accrued, we would like to broaden the study.

In the proposed study, we will continue to advance the eRFA. We will assess whether performing eRFA along with *automated recommendation* for each eRFA impairment is feasible, and to collect preliminary data on its impact of patients' surgical outcomes and functional recovery compared to in-person geriatric co-management.

Our intervention, if feasible, will be scalable, and will likely improve care for hundreds of thousands of older cancer patients who are evaluated every year for their fitness for undergoing surgery.

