Following completion of the eRFA, the summary of impairments as well as the recommendations generated by the study team (hard-copy or email) will be provided in real-time to the thoracic surgery team for their attention. A sample is provided below. In this case, patient has impairments in various domains that ranges from KPS to number of medications.

[eRFA Summary](#)

Global recommendation: If 3 or more impairments are listed in the summary below, consider referral to geriatrics.
T = Threshold | **P** = Percentile | **PS** = Patient Score

KPS  More Information:	T: ≤ 80	P: 37%	PS: 60.
ADL  More Information:	T: < 14	P: 52%	PS: 12.
iADL  More Information:	T: < 16	P: 45%	PS: 13.
Timed Up and Go Test  More Information:	T: ≥ 10 seconds	P: 36%	PS: 10-19 seconds.
Social Support  More Information:	T: ≤ 16	P: 43%	PS: 16.
Limited Social Activity  More Information:	T: ≥ 8	P: 50%	PS: 12.
Weight Change  More Information:	T: 10 pound loss or more	P: 16%	PS: 10-20.
Distress Level  More Information:	T: ≥ 4	P: 55%	PS: 7.
Number of Medications  More Information:	T: ≥ 5	P: 45%	PS: More than ten.

Subsequently, the research staff member clicks on various impairments and would be able to view and print the recommendations for each impairment. For example, the following are the recommendations for a Timed Up and Go test impairment.

Timed Up and Go Test **T:** ≥ 10 seconds **P:** 36% **PS:** 10-19 seconds.

[More Information:](#)

[Pre/Postop Recommendation:](#)

- A- Consider consultation with physical therapy and occupational therapists.
- B- Encourage use of appropriate assistive devices.
- C- Encourage resistance exercises such as repeated chair stand in the preoperative period.
- D- Consider use of stationary bike or bike pedals in the preoperative period.

[Medical Recommendation:](#)

[Education:](#)

[Supportive Services:](#)

A copy of the recommendations will be available in EMR. After preoperative clearance by patients' primary care providers, general internal medicine service, or other services such as cardiology, patients will undergo surgery. The geriatrics service will see patients before or after surgery if the consult is requested by the surgery service. The automated co-management program is not expected to lengthen the patients' first visits.

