7.1 ASSESSMENT/EVALUATION PLAN

Assessment and Measurement Instruments:

In this study, the data will be collected using the following instruments and measurements methods:

- Electronic Medical Record review:

- 1- For patients in the intervention group (automated geriatric co-management), we will assess the percentage of recommendations that were followed by the surgery team. For example, if automated geriatric co-management recommends consultation with physical therapy perioperatively, we will assess whether the consult has been obtained.
- 2- For patients in both groups, we will assess the adverse surgical events by day 30 following surgery. Adverse surgical event is a composite of surgical complications grade 2 or higher, mortality after surgery, or discharge to any place other than home, or prolonged length of stay (defined as length of stay longer than 75% of the cohort who underwent the same surgical procedure), or readmission to the hospital within 30 days from surgery.

MSKCC's secondary surgical events database in the EMR has been shown to accurately record major postoperative complications within the 30 days after surgery[34].

- 3- to assess sociodemographic characteristics (age, gender, ethnicity),
- 4- to assess routine preoperative blood work (complete blood cell counts, chemistry panel).
- 5- To assess cancer characteristics (stage, receipt and type of neoadjuvant treatment)

- 6-** To assess surgical characteristics (type of surgery: minimally invasive vs open, duration of surgery, intraoperative blood loss, and American Society of Anesthesiologist Physical Status classification)
- **Four Meter Walk Test:** In order to assess functional recovery, the 4-meter walk test will be performed. In the 4-meter walk test, the time that it takes patients to walk 4 meters in their usual pace will be recorded in seconds by the clinical research staff. (This portion will be skipped for patients being seen via telemedicine.)

Assessment and Evaluation Plan

Patients will be screened for study eligibility at the time of attending their surgery appointment at MSKCC for consideration of surgery. The inclusion and exclusion criteria will be reviewed by the clinical research staff firstly to confirm the patients' eligibility status. Once eligibility has been determined and informed consent has been obtained, patients will undergo baseline assessments and subsequently randomization will occur.

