9.0 PRIMARY OUTCOMES

	Baseline study visit	Preoperative visit (if two months have passed by from baseline study visit)	2 nd study visit	30-day post-surgery follow up
eRFA (including Karnosky Performance Status, basic Activities of Daily Living, instrumental Activities of Daily Living, Timed-up-and-Go test)	✓	✓	✓	
4 MWT	✓	✓	✓	
Sociodemographic characteristics	✓			
Preoperative lab results				✓
Cancer characteristics				✓
Surgical characteristics				✓
Adverse events				✓
Hospital Length of Stay				✓
Discharge/Disposition location				✓
30-day readmission to hospital				✓
Number of geriatric recommendations followed				✓

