To compare, by intervention arm, postoperative functional recovery. We will consider postoperative functional recovery as reported by the patient, as well as assessed by the study team during the 2nd study visit. Patient-reported recovery will be measured by three domains reported on both pre and post-operatively: Karnofsky Performance Status, basic activities of daily living, and instrumental activities of daily living.

Clinician-evaluated functional recovery will be assessed through the Timed Up and Go

test and the 4MWT. This analysis will only be done for patients who have completed the assessment during in-person visit with the surgery team. Recovery of Karnofsky Performance status, defined as the same or better Karnofsky Performance status during the 2nd study visit compared to baseline, will be compared between groups using a logistic regression with randomization strata as covariates. Basic activities of daily living, instrumental activities of daily living, Timed up and Go test and 4MWT will be compared between groups by ANCOVA, with baseline score and randomization strata as a covariate.

In the case that patient's surgery occurs after two months of completing the eRFA, either the patient has to complete another eRFA within two months of surgery, which then will be the patient's new preoperative baseline eRFA, or in case of not completing the eRFA, the patient will be excluded from the study.

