We are additionally interested in using the three components, of the patient-reported functional recovery in three categories: complete recovery (defined as all three post-operative measurement score being greater than or equal to the pre-operative measurement score), partial recovery (defined as at least one, but not all three, post-operative measurement scores being greater than or equal to the pre-operative measurement score), or no recovery (defined as none of the post-operative measurement scores being greater than or equal to the pre-operative measurement score). Similarly we will use two components of the clinician-evaluate functional recovery to define three categories: complete recovery (defined as all both post-operative measurement score being greater than or equal to within 10% of the pre-operative measurement score), partial recovery (defined as at least one, but not both, post-operative measurement scores being greater than or equal to within 10% of the pre-operative measurement score), or no recovery (defined as neither of the post-operative measurement scores being greater than or equal to within 10% of the pre-operative measurement score). We will test the association between intervention arm and degree of recovery by using ordinal regression with randomization strata as covariates.

As it is likewise plausible that the relative value of in-person vs. automated geriatric co-management depends on baseline risk, we will repeat the analysis described above, related to baseline risk, for the outcomes of patient-reported functional recovery and clinician-assessed functional recovery.

Sample size

With a null hypothesis of 55% and the alternative hypothesis of 70% of patients with recommendations followed, and a one-sided α of 5% and a power of 85%, we require 77 eligible patients to be accrued in the automated geriatric co-management arm for a two-stage Simon minimax design. We expect about 25% of patients to be excluded for the primary aim due to no impairment (5%) or crossover to the in-person

geriatric comanagement arm (20%) suggesting a total accrual close to 100 per group.

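### The plan does not say that Timed Up and Go seconds are kept for analysis; the only source it describes shows three bands, from which the within-10% recovery rule cannot be computed

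*Combined protocol and SAP*

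**What the plan says.** **How TUG is captured.** In Section 3.1, Figure 2, the TUG row describes a timed test and states "The total time is recorded". The score range in that row is "<10 seconds, 10-19 seconds, ≥ 20 seconds". The text on administering the eRFA says of the nurse's Mini-Cog and TUG that "the results of which are then entered into the eRFA by the RN". The sample eRFA summary in Section 4.2, repeated in Section 4.3, shows the patient's TUG score as "PS: 10-19 seconds".

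**Where else TUG appears.** The Section 9.0 table lists it only inside the eRFA row: "eRFA (including Karnosky Performance Status, basic Activities of Daily Living, instrumental Activities of Daily Living, Timed-up-and-Go test". The visit assessments in Section 7.1 name the 4-meter walk test (4MWT) and the eRFA, with no separate TUG item. By contrast, Section 7.1 is explicit for the 4MWT: "the time that it takes patients to walk 4 meters in their usual pace will be recorded in seconds by the clinical research staff".

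**How TUG is analysed.** Section 11.0 states "Timed up and Go test and 4MWT will be compared between groups by ANCOVA, with baseline score and randomization strata as a covariate". It then combines TUG and 4MWT into complete, partial or no clinician-evaluated recovery. Each component is judged by "post-operative measurement score being greater than or equal to within 10% of the pre-operative measurement score", and the arms are compared by ordinal regression.

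**The concern.** Both planned analyses presume a time in seconds, but the described data path ends in a three-level category. TUG is one of only two components of clinician-evaluated recovery. If only the band survives, that composite, its ordinal regression and the repeat analysis by baseline risk cannot be carried out as defined. The separate TUG comparison also becomes coarser. The trial is meant to supply preliminary data on functional recovery for a later study, and seconds not retained at a visit cannot be recovered afterwards.

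**Working it through.** **1. Is the band the recorded value?** The sample summary prints numeric items as exact scores (KPS 60, ADL 12, iADL 13). Items that Figure 2 scores in ranges are printed as ranges: weight change 10-20, medications more than ten, TUG 10-19 seconds. This fits band entry for TUG but does not prove it, because the Figure 2 row also says the total time is recorded.

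**2. Can the 10% rule be computed from bands?** Take recovery as follow-up time no more than 1.10 times baseline time, since a longer time is worse. Nine baseline/follow-up band pairs are possible.

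| Change | Follow-up ÷ baseline | Rule decided? |
|---|---|---|
| Same band (3 pairs) | middle band, whole seconds: 10/19 = 0.53 to 19/10 = 1.90 | no |
| <10 to 10–19 | from 10.0/9.9 = 1.01 upward | no |
| 10–19 to ≥20 | from 20/19 = 1.05 upward | no |
| <10 to ≥20 | above 20/10 = 2 | yes, not recovered |
| Any faster band (3 pairs) | below 1 | yes, recovered |

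Five of the nine pairs are undecided, including every pair with no change of band. Two examples: 10 s to 19 s is 19/10 − 1 = +90% with no change of band, while 9.5 s to 10 s is 10/9.5 − 1 = +5%, inside the margin, and crosses a band. The direction of the inequality in Section 11.0 is a separate matter. Read literally (follow-up at least 0.90 times baseline), the rule is still undecided within a band, because 0.53 to 1.90 straddles 0.90 as well.

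**3. The plan's own ANCOVA power.** Inputs from Section 11.0: SD 1.8, correlation 0.5, 95 per arm. No alpha is given for that table, so two-sided 0.05 is assumed.

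- Adjusted SD = 1.8 × √(1 − 0.5²) = 1.559
- Standard error = 1.559 × √(2/95) = 0.226
- Power = Φ(difference/0.226 − 1.96)

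| Difference | Computed | Stated |
|---|---|---|
| 0.5 | 59.9% | 60% |
| 0.67 | 84.2% | 84% |
| 0.8 | 94.3% | 94% |

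The table reproduces. However, its SD comes from basic activities of daily living, so it says nothing about TUG in seconds or in bands.

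**4. What do bands cost the ANCOVA?** The documents give no TUG distribution, so this is an illustration only. Assumptions: log-normal TUG, median 9, 11 or 14 s, log-SD 0.25 or 0.35, correlation 0.5, 95 per arm, a group difference of 0.10 on the log scale (about 10%), no strata in the model, 2,000 simulated trials per setting. Bands were coded 0/1/2.

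| Log-SD | Power, seconds | Power, band codes |
|---|---|---|
| 0.25 | 86–87% | 58–63% |
| 0.35 | 57–59% | 42–43% |

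With no true difference, rejection rates were 4.3–6.0% on seconds and 4.4–5.8% on codes. With 2,000 trials the simulation error at 5% is √(0.05 × 0.95/2000) = 0.5 points, so both are consistent with 5%.

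**The case against.** The strongest reply is that the seconds may well exist. The Figure 2 row says the total time is recorded, and its bands stand beside the frailty cut-off. The sample summary is a clinician-facing report, not a data dictionary. Section 13.1 sends study data to a REDCap database whose fields are not shown, and Section 3.1 says the eRFA changed platform during the study. A reader might infer from the bands that the seconds have been discarded. The documents do not support that: storage in bands alone is a strong inference, not a statement. What remains is that no section says where seconds are kept, and the one source that is described shows bands.

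A reader might also infer that ANCOVA on three levels is invalid. It is not. It can be run, and the false-positive rate stays near 5% in the illustration. The loss is in precision and in an estimate expressed in seconds.

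Finally, the reach is limited. TUG serves one secondary aim of a self-described pilot and is analysed only in patients assessed in person. The feasibility aim and its 77 patients, adverse surgical events and patient-reported recovery do not depend on it. This limits the priority of the point but does not remove it.

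**Conclusion.** The point holds as a mismatch between described data capture and planned analysis. If only bands are available, the 10% rule cannot be applied to most band pairs. The clinician-evaluated composite then cannot be formed as defined, a result that follows from arithmetic alone. The ANCOVA remains possible at lower precision. The power losses shown rest on assumed TUG distributions and on 95 per arm, which is the plan's figure before telemedicine visits are excluded. They indicate direction, not a forecast. No percentage of patients wrongly called recovered should be quoted, because that figure depends on a TUG distribution and an amount of postoperative slowing that the documents do not give. If seconds are in fact retained, a sentence saying so settles the matter. The plan should be corrected before analysis, but the trial's primary conclusion is not at risk.

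**What to change.** - Capture TUG in seconds as a numeric field, in the eRFA or REDCap, at baseline/pre-op and at the second visit. If this is already done, state where.
- State in Section 11.0 that the ANCOVA and the 10% rule use seconds. Keep the bands only for the impairment flag.
- For patients already recorded only in bands, analyse TUG by ordinal regression adjusted for baseline band and randomization strata.
- Treat those patients' clinician-evaluated composite as missing, with the planned multiple imputation as sensitivity analysis. Do not build it from the 4MWT alone: with one component, partial recovery (one but not both) is impossible, and the outcome would mean different things for different patients.

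The cost is one added field and a short addition to Section 11.0. The nurse already times the test, so no test or visit is added. The drawback is fewer patients in the composite if earlier records hold bands only.
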